#### **Incomplete dates for adverse events and medications**

For analysis of AEs and medications, a complete date should be established in order to identify AEs or medication as occurring during treatment or not. For the purpose of handling partially reported start and stop dates for AEs or medication the following algorithm will be applied:

- Missing start day, but month and year present:  
If trial medication had been taken in the same month and year as the occurrence of the AE/medication, then the start day of the event/medication will be assigned to the day of first dose of trial medication.  
Otherwise the start day will be set to the first day of the month.
- Missing start day and month, but year present:  
If trial medication had been taken in the same year as the occurrence of the AE/medication, then the start date of the event/medication will be assigned to the date of first application of trial medication.  
Otherwise the start day and month will be set to 01 January.
- Missing end day, but month and year present:  
The day will be set to the last day of the month.
- Missing end day and month, but year present:  
The end day and month will be set to the date of trial termination.  
However, if trial termination year is greater than the year of the event/medication, then the day and month will be set to 31 December.

In subject data listings, start and stop date of AEs or medication will be displayed as reported.

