#### **11.5. Concomitant Medications**

Medications received prior to the date of first dose are considered as prior medications. Medications will be considered as concomitant if the start date of the medication is on or after the date of first intake of study drug or if the start date is prior to the first date of study drug but the medication is ongoing during the treatment period in the study.

Medication verbatim text will be coded using the World Health Organization (WHO) Drug Dictionary. Use of non-study medications will be summarized (number and percentage of subjects) by treatment and WHO preferred name. Multiple drug use (by preferred name) will be counted once only per subject. No inferential statistics will be provided.

Medications that were used for HAE related indications will be summarized separately (plasma-derived C1-INH Berinert, Cinryze will be combined together). Medication data will be listed.

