## **12.4. Adverse Events**

All AEs will be coded using the Medical Dictionary for Regulatory Activities (MedDRA 18.1). System organ class (SOC), high level group term, high level term, preferred term, and lower level term will be attached to the clinical database. A table showing the mappings of AE verbatim text to the coded terms will be provided.

Adverse events with an onset date and time prior to the first dose of study drug for the study will be assigned as a pre-dose AE for the listing and will not be included in the summaries.

Treatment-emergent AEs are defined as AEs that occurred on or after date of first dose of study drug and up to +30 days after the last dose. Investigators are not required to contact subjects after the last follow-up if it occurs prior to 30 days from last dose.

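### SAP 10.1 imputes partial start dates without checking a known stop date, so some records that ended before dosing are counted as treatment-emergent or concomitant

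*SAP*

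**What the plan says.** SAP 10.1, under incomplete dates for adverse events and medications, gives two start-date branches, each with a condition and a fallback.

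- **Day missing, month and year known.** The condition is "If trial medication had been taken in the same month and year as the occurrence of the AE/medication". If it is met, "then the start day of the event/medication will be assigned to the day of first dose of trial medication". If not, "Otherwise the start day will be set to the first day of the month".
- **Day and month missing, year known.** The condition is "If trial medication had been taken in the same year as the occurrence of the AE/medication". If it is met, "then the start date of the event/medication will be assigned to the date of first application of trial medication". If not, "Otherwise the start day and month will be set to 01 January".

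Two later sections use the resulting date. SAP 12.4 states: "Treatment-emergent AEs are defined as AEs that occurred on or after date of first dose of study drug", with an upper limit 30 days after the last dose. Events with an earlier onset are labelled pre-dose and left out of the summaries. SAP 11.5 states: "Medications will be considered as concomitant if the start date of the medication is on or after the date of first intake of study drug". A drug with an earlier start is concomitant only if it was still being taken during treatment.

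SAP 10.1 also says that listings show the dates as they were reported, so the imputed date acts only on classification and on the tables.

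**The concern.** The purpose of the algorithm is to decide whether a record belongs to the treatment period. When the stop date is known and lies before first dose, that question is already answered: the record is pre-dose. The rule does not use this information. It can assign a start on the day of first dose to something that had already ended, which produces an impossible interval and the wrong class.

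The trial collects records of this kind. AEs are recorded from consent (Protocol 12.1.2), and screening may be up to 21 days before Day 1 (Protocol 10.3.1). Medications are recorded from 60 days before screening (Protocol 9.7). Resolved screening-period AEs and drugs stopped before dosing will therefore be in the database.

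At stake are the treatment-emergent AE tables and the concomitant-medication tables, including the separate summary of drugs used for HAE-related indications. In those, a drug stopped before dosing would appear as used on study.

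**Working it through.** The plan gives no figure to reproduce. The check is to apply the rule as written to test records and then classify them under SAP 12.4 and 11.5.

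**Inputs**

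- Assumed first dose: 20 Sep 2016. This is illustrative and not from the documents.
- Dosing lasts 28 days (Protocol synopsis), so last dose = 20 Sep + 27 days = 17 Oct 2016.
- Treatment-emergent window (SAP 12.4): 20 Sep to 17 Oct + 30 days = 16 Nov 2016.
- Earliest screening: 20 Sep − 21 days = 30 Aug. Medication look-back from there: 30 Aug − 60 days = 1 Jul. A drug stopped on 15 Jul can therefore be on record.
- The phrase *day of first dose* is read as the first-dose date.

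**Rule.** If any dose falls in the reported month and year (or in the reported year, when only that is known), start = 20 Sep 2016. Otherwise start = first of the month, or 1 January.

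**Check added.** If stop < first dose, start = first of the reported month (or 1 January), and the record stays pre-dose or prior.

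| # | Record | Reported start | Stop | Start under 10.1 | Class as written | Class with stop-date check |
|---|---|---|---|---|---|---|
| 1 | AE | Sep 2016 | 12 Sep 2016 | 20 Sep 2016 | treatment-emergent | pre-dose |
| 2 | Drug | Sep 2016 | 10 Sep 2016 | 20 Sep 2016 | concomitant | prior |
| 3 | Drug | 2016 | 15 Jul 2016 | 20 Sep 2016 | concomitant | prior |
| 4 | AE | Aug 2016 | 2 Sep 2016 | 1 Aug 2016 | pre-dose | pre-dose |
| 5 | Drug | 2015 | 15 Jul 2016 | 1 Jan 2015 | prior | prior |
| 6 | AE | Oct 2016 | 25 Oct 2016 | 20 Sep 2016 | treatment-emergent | treatment-emergent |

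Records 1 to 3 are given starts 8, 10 and 67 days after their own stops (20 − 12; 20 − 10; 16 + 31 + 20), and all three are misclassified. The stop-date check restores them and changes none of the other three.

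Records 4 and 5 show the fallbacks working. Record 6 shows a separate wording fault. The condition tests against any month in which drug was taken, not the month of first dose, so an October event is dated in September. If the phrase instead means the day number, the same event lands on 20 Oct, after the last dose. Its class is the same either way. Every day of the second dosing month is after first dose, and because that month contains the last dose, its final day is at most 30 days later (day 1 to day 31).

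**When the fault occurs.** With only the day missing, the record must start and end in the month of first dose, before the first-dose day. With day and month missing, it must start and end before first dose within the year of first dose.

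**Scale of one error.** Protocol 5.4.1.3 expects 6 subjects on 62.5 mg in Part 3. One subject wrongly counted for a given AE term moves that group's incidence by 1/6, about 17 percentage points, provided the subject has no genuine event under that term.

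**The case against.** The best defence is that the rule is deliberately conservative. When timing is uncertain, it counts the event on treatment, in the same spirit as Protocol 13.2.5, which treats a Day 1 AE without an onset time as treatment-emergent. It applies alike in every arm, hides no event and feeds no test: the SAP plans no inferential statistics for AEs or concomitant medications. Attack dates have their own imputation rule, so efficacy is untouched. Listings keep the reported dates, deviations go to a data review meeting, and SAP 11.3 allows rules for missing or unclear data to be refined. The triggering pattern is narrow, and nothing in the documents shows it to be frequent.

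Most of this stands, and it limits the size of the point. It does not remove it. The conservative argument covers events whose timing is unknown, and here the stop date settles the timing. Permission to revise is not a correction, and no other section supplies one.

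Three stronger readings are tempting and are not supported.

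- A reader might infer that every partial date is moved to first dose, or that the reported month is ignored. The conditions and fallbacks say otherwise, as records 4 and 5 show.
- A reader might infer that events dated to the second dosing month are misclassified. They are misdated only.
- A reader might infer that the liver tables split by prior androgen use are contaminated, or that prohibited prophylaxis would be wrongly established. The source of the androgen flag is not stated, and HAE medication history is captured on its own questionnaire (Protocol 11.1.2). Prohibited medications are checked at screening and on Day 1, and the sponsor reviews past and concomitant medications before randomization.

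**Conclusion.** The rule is wrong as written for one defined class of record: a partial start in the same month and year as first dose (or the same year, if only the year is known) with a stop before first dose. Each such record receives a start after its own stop and is counted as treatment-emergent or concomitant.

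The consequence is limited to descriptive AE and concomitant-medication tables, including the HAE-medication table. A table may also disagree with its listing, which would show the reported stop before dosing. The number of affected records cannot be estimated, because the documents give no count of partial dates. In the smallest dose group a single record could be visible.

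The conclusion rests on the rule being programmed literally, with no ordering check added in code. The 20 Sep 2016 date is only an illustration; the fault follows from the wording for any first-dose date that leaves room before it in the month or year.

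**What to change.** Add to SAP 10.1, for both start-date branches:

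- If the stop date, complete or partial, shows that the record ended before first dose, set the start to the first day of the reported month (or 1 January of the reported year) and keep the record pre-dose or prior. A partial stop counts only if its latest possible date is before first dose.
- An imputed start may never fall after the stop date.

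As a secondary wording change, state that the day of first dose means the first-dose calendar date. Apply it only when the reported month, or the reported year, is that of first dose; otherwise use the first day of the reported month or year. This corrects the imputed date and leaves treatment-emergent and concomitant status unchanged.

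The cost is a sentence or two in the SAP and a few lines of code. No data collection changes, and SAP 11.3 already allows refinement of this kind.

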#### **Missing time of last dose**

In case the time of the last dose is not reported, time of dose will be assigned as the median dosing time for the subject.

#### **Incomplete date and time for a subject-reported attack**

For HAE attacks reported with a missing stop date and or time, the following algorithm will be applied:

- Missing start time but start date present:  
The start time will be set to 12:00PM.
- Missing start date and time:

The start date will be set to the date for which the question was answered “Yes”. The start time will be set to 12:00PM

- Missing stop time, but stop date present:

The stop time will be set to 11:59PM

- Missing stop date and time:

The stop date will be set to the attack start date, the stop time will be set to 11:59PM

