#### **9.4. Study Drug (Investigational Medicinal Product) Administration and Treatment Compliance**

Subjects will take all study drug doses at home with the exception of study drug that will be administered under Investigator (or designee) supervision during scheduled on-treatment clinic visits on Days 1, 14 and 15 (and Day 28 if applicable). Subjects will be instructed to take 3 capsules (Parts 1 and 2) or 2 capsules (Parts 3 and 4) of study drug orally QD in the morning for 28 days. Subjects will be instructed to take study drug with food, or within 30 minutes after consuming food. On Days 1, 14 and 29, subjects should fast for 8 hours prior to their blood draw for laboratory testing.

The first dose of study drug will be administered in the clinic on Day 1. For study Days 14 and 15, subjects should be instructed to refrain from taking study drug prior to their visit to obtain a trough and/or serial blood draws at steady state.

On in-clinic dosing days (Days 1, 14 and 15), subjects will be required to consume food within 30 minutes prior to dosing (but after any blood draws for safety laboratory testing); the requirements for type and amount of food is to be provided to the subject (e.g., number of

servings of protein, carbohydrate, and/or fat) will be communicated in a separate document. On all other days, subjects should take the study drug in the morning with food (or within 30 minutes after consuming food). It is recommended that the study drug be administered with food in order to help minimize gastrointestinal effects. If gastrointestinal-related symptoms are noted as an AE, the site should query the subject and record whether the drug is being taken as instructed (i.e., with food).

Subjects will be instructed to maintain approximately the same daily dosing interval between study drug doses. If a subject forgets to take the study drug at the correct time, the dose may be taken later in the day; however, no more than 1 dose of BCX7353 should be taken on any calendar day. The subject should resume the standing regular dosing schedule on the next day.

Subjects will be instructed to record in their diary the time of day study drug was taken, and the number of capsules of study drug taken.

Subjects will be instructed to bring all drug kits (including both unused and used kit bottles) and diaries with them for each study visit. Accountability and adherence will be reviewed at each clinic visit.

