### **10.8.5. Attack Onset Relative to Prior Dose of Study Drug**

For each confirmed attack, the time to attack onset from the time of the prior dose of study drug reported in the subject CRF page will be calculated. If there is no dosing time reported for the dose taken prior to the attack, the attack will not be included in the attack onset analyses.

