The time to first attack after the last dose will be summarized descriptively and graphically using Kaplan-Meier method. The Kaplan-Meier (KM) estimate for the median, and the first and third quartiles will be determined along with approximate 95% confidence intervals. Brookmeyer-Crowley method will be used for the confidence interval calculation. Subjects who do not have an attack will be censored at the date of last follow-up assessment for the KM analysis.

- Time to treatment

The time to treatment defined as the time from the start of an attack to the use of the first HAE medication reported in the diary will be derived for each attack and summarized by treatment, by country and site at attack level.

The time to first HAE medication will also summarized graphically using KM method. The KM estimate for the median and the first and third quartiles will be determined along with approximate 95% confidence intervals. Brookmeyer-Crowley method will be used for the confidence interval calculation. Subjects who do not take medication will be censored at end of the attack.

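### Attack start times imputed at noon stay in the onset-relative-to-dose analysis, and nothing stops them producing negative times to treatment

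*SAP*

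**What the plan says.** **Imputation.** Where an attack has a start date but no start time, SAP 10.1 says "The start time will be set to 12:00PM". If the date is missing as well, "The start date will be set to the date for which the question was answered" (that is, answered yes), again with 12:00PM. A missing stop time is handled by "The stop time will be set to 11:59PM". Because 11:59PM serves as the end of the day, 12:00PM means noon. The sentence introducing these rules is narrower than the bullets beneath it: "For HAE attacks reported with a missing stop date and or time, the following algorithm will be applied".

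**Where the start time is used.**
- SAP 10.8.5 calculates "the time to attack onset from the time of the prior dose of study drug". Its only exclusion is for an attack whose prior dose has no recorded time.
- SAP 10.8.4 takes attack duration as stop minus start.
- SAP 12.1.4 defines time to treatment as "the time from the start of an attack to the use of the first HAE medication reported in the diary", summarised by attack and by Kaplan-Meier.

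**Dosing.** Under Protocol 9.4, subjects take "study drug orally QD in the morning for 28 days". No clock time is given.

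**Status.** Onset relative to the last dose is a secondary endpoint (Protocol 7.2.2, SAP 2.2.2) and is among the comparisons with placebo listed in SAP 7.2, if data permit. The sensitivity analyses in SAP 12.1.3 deal with missing diary days and subject-reported attacks, not with imputed start times.

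**The concern.** The onset endpoint is a difference between two clock times. When the dose time is unknown, the SAP treats the difference as unknown and drops the attack. When the start time is unknown, it inserts noon and keeps the attack, although that inserted value then determines the result. With morning dosing, noon is not spread over the dosing interval: it is a single point a few hours after the dose. An attack that truly began at 05:00 in a subject who doses at 08:00 started 21 h after the prior dose (24 - 3), yet the rule records 4 h (12 - 8).

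The same noon value is subtracted from recorded medication and stop times, and nothing requires it to precede them. What is at stake is the shape of the onset distribution within each arm and the validity of the time-to-treatment summary. A negative time has no meaning in a Kaplan-Meier analysis, and the SAP does not say what would be done with one.

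**Working it through.** The plan states no figure on this point, so there is none to reproduce. The check is clock arithmetic.

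**Inputs from the documents**
- Imputed start: 12:00 noon (SAP 10.1).
- Dosing: once daily, morning (Protocol 9.4).
- Time to peak concentration: about 2 to 5 h in fasted Western healthy subjects and 2 to 6 h in Japanese healthy subjects (Protocol 5.3.1).
- Medication times are recorded in the diary (Protocol 11.2.2).
- Symptoms typically subside over 3 to 5 days (Protocol 5.1).

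**Assumptions, not in the documents**
- Dosing hour: 06:00 to 11:30.
- Share of start times imputed, m: 5% to 30%.
- True onset uniform over 24 h, with the start date correct.

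**1. Where noon falls.** Hours after dose = 12 - dose hour.

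| Dose taken | Noon is |
|---|---|
| 06:00 | 6 h after |
| 07:00 | 5 h after |
| 08:00 | 4 h after |
| 09:00 | 3 h after |
| 10:00 | 2 h after |
| 11:00 | 1 h after |
| 11:30 | 0.5 h after |

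Noon lies in the 2 to 5 h window for doses from 07:00 to 10:00 and outside it otherwise.

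**2. Share of onsets in the 2 to 5 h window**, for a dose in that range: m + (1 - m) × 3/24.

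| Imputed | Share in window |
|---|---|
| 0% | 12.5% |
| 5% | 0.05 + 0.95 × 0.125 = 16.9% |
| 10% | 0.10 + 0.90 × 0.125 = 21.3% |
| 20% | 0.20 + 0.80 × 0.125 = 30.0% |
| 30% | 0.30 + 0.70 × 0.125 = 38.8% |

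A simulation with an 08:00 dose gave 12.4%, 21.2%, 30.1% and 38.9% at 0%, 10%, 20% and 30%. Excluding the imputed attacks returns the expected share to 12.5%.

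**3. Negative intervals.** Let T be the true hours from onset to the recorded event. The interval is negative when the event precedes noon, with probability max(0, 12 - T)/24 among imputed attacks.
- Time to treatment: T = 1, 2, 4 h gives 11/24 = 46%, 10/24 = 42%, 8/24 = 33%.
- Duration, with a recorded stop: T = 2, 6, 8 h gives 42%, 25%, 17%; at 12 h or more it is 0%.

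Example: true start 06:00, medication 07:30, stop 11:00. Time to treatment is 7.5 - 12 = -4.5 h, and duration is 11 - 12 = -1 h.

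**4. Dependence on the introductory sentence.** Read literally, the rules apply only when stop information is missing. The -1 h duration above has a recorded stop, so it needs the wider reading that the start-time bullets imply. The negative time to treatment arises on either reading. Even on the literal reading, a negative duration is possible. The diary asks about the last 24 hours, so a start date set to the reporting day can fall after a recorded stop date one day earlier: from noon back to 23:59 the previous day is -12 h 1 min. If the start time and all stop information are missing, duration is always 23:59 - 12:00 = 11 h 59 min.

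**The case against.** **Missingness may be low.** Under Protocol 11.2.2, staff check diaries on Days 1, 7, 14, 21 and 29 and may ask subjects to correct incomplete entries. The documents give no missing rate. This stands: the percentages above are conditional on assumed rates.

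**Noon is a neutral choice.** As the midpoint of an unknown day, it is reasonable for a duration. It is not neutral for an interval measured from a morning dose, and it still needs a bound where a recorded event comes earlier.

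**The peak is modest.** The times to peak come from healthy subjects, the 2 to 5 h figure from fasted ones, whereas this trial doses with food. At 250 mg for 7 days in Western subjects, peak over average concentration is 217/(3710/24) = 1.4. Protocol 5.3.3.2 reports inhibition sustained above 75% over the interval at 250 and 350 mg; only 125 mg shows a clear fall, from about 60% to about 40%. This stands against reading much pharmacology into where the imputed values land. It does not make an invented interval informative.

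**Stronger readings that the documents do not support.**
- A reader might infer that the endpoint exists to detect attacks clustering at trough and that noon imputation hides them. No section gives it that purpose, and at 5% to 10% imputed most onsets keep their reported times, so a real pattern would be diluted rather than hidden.
- A reader might infer a bias between arms. The rule applies equally to all arms, and nothing suggests that missingness differs by arm.
- A reader might infer that SAP 10.1 contradicts 10.8.5 because it fills a missing last-dose time with the subject's median. That rule may concern only the final dose, which is needed for the cut-off 24 h after the last dose in SAP 10.6. Because SAP 2.2.2 also uses the term last dose for the onset endpoint, this is an ambiguity, not a shown conflict.

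**The SAP can be refined.** SAP 11.3 reserves changes to missing-data rules. It leaves room for this correction but does not make it.

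**Conclusion.** The point holds for secondary and additional summaries. As written, the SAP keeps onset intervals determined by an imputed clock time while discarding those with a missing dose time, and it permits negative times to treatment.

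The distortion is within arm and common to all arms. For doses between 07:00 and 10:00 and uniform true onset, the 2 to 5 h share rises from 12.5% to 21.3% at 10% imputed, with a range of 16.9% to 38.8% over 5% to 30%. Dosing hour, uniformity and missing share are all assumptions. For doses outside those hours the artificial spike remains but sits elsewhere.

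Negative times to treatment are the likelier impossible value. Negative durations from a recorded stop need the wider reading of SAP 10.1 and should be uncommon given the 3 to 5 day course.

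A reader might also infer that the primary attack count is at risk. The one visible route is narrow: an attack on the morning after the last dose with no start time could be placed at noon, beyond a morning cut-off under SAP 10.6. That does not support a general claim about the primary endpoint.

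**What to change.** - **Onset relative to dose, and time to treatment:** exclude attacks with an imputed start time and report the number excluded by arm.
- **Duration:** set the imputed start to the earliest of noon, the first recorded medication time and the recorded stop time, comparing date and time together. No negative value can then arise. A zero duration remains possible where the stop is the earliest of the three.
- **SAP 10.1 introductory sentence:** reword it to cover missing start times as well as missing stop information.
- **Missing dose time:** state whether the median-time rule in SAP 10.1 applies only to the final dose or also to the prior dose in 10.8.5.

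The cost is SAP wording. A few attacks drop out of two secondary or additional summaries; no data collection changes.

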#### Study Conduct Overview

Following an up to 21-day screening period, eligible subjects, who have had entry criteria confirmed by the Sponsor, will be dosed on Day 1. Subsequent clinic visits will be held on Days 7, 14, 21 and 29. At the Day 14 visit, subjects will also have serial blood samples drawn immediately prior to and after the dose, including a visit on Day 15 for collection of a 24-hour postdose PK sample. A follow-up visit will be performed on Day 44.

Subjects will record the occurrence and details of all angioedema attacks at least once daily beginning from the date of screening until the follow-up visit. On Days 1 through 28, subjects will also record the time of day that the study drug (BCX7353 or placebo) was taken and the number of capsules of study drug taken at each dose. Subject-reported study drug administration and HAE attacks will be captured in a diary.

During the study, each subject will continue to use their prescribed acute attack medication to treat any attacks, under the medical management plan advised by their physician. All participants must have access to effective, approved acute treatments for attacks of angioedema as part of their routine medical care.

Subjects will only participate in one part of the study.

All subjects who successfully complete treatment in the study will be offered the opportunity to participate in a future long-term study of BCX7353 where locally approved, provided that development of BCX7353 continues.

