## 5. INTRODUCTION

### 5.1. Background

Hereditary angioedema (HAE) is an autosomal dominant disorder characterized by recurrent episodes of swelling of the skin, pharynx, larynx, gastrointestinal tract, genitals, and extremities (Longhurst and Cicardi 2012). The frequency of attacks varies between subjects, from rarely in some patients to every few days in others. Angioedema attacks may or may not be precipitated by a stimulus (such as stress, trauma, or estrogen) and are typically rapid in onset, with symptoms subsiding gradually over the following 3 to 5 days (Zuraw and Christiansen 2011). Oropharyngeal swelling can be life-threatening (Bork, Hardt et al. 2012), while attacks in other sites, including limbs, genitalia, face and intestines, can be painful, disabling, and disfiguring, and have a significant impact on functionality and quality of life (Lumry, Castaldo et al. 2010). Although mortality risk from asphyxiation is much higher in undiagnosed patients with HAE, deaths still occur in diagnosed patients with access to care at centers of excellence (Bork, Hardt et al. 2012).

Extensive evidence from animal models and clinical studies supports the role of bradykinin (BK) as the principal mediator of the signs and symptoms that characterize attacks of HAE (Kaplan 2010, Zuraw and Christiansen 2011). Plasma kallikrein is a serine protease integral to the contact activation pathway (Saxena, Thompson et al. 2011). Kallikrein circulates in plasma as a zymogen, prekallikrein (PKK), bound to one of its main substrates, high-molecular-weight kininogen (HK). During contact activation, PKK is cleaved by activated factor XII, forming the active protease kallikrein. Kallikrein in turn cleaves HK, producing BK (Kaplan and Ghebrehiwet 2010). The activation of the bradykinin B2 receptor by BK ultimately results in vasodilatation, increased vascular permeability, and smooth muscle contraction, all of which lead to the tissue swelling that characterizes HAE (Kaplan 2010).

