### **11.2.2. HAE Attack and Dosing Diaries**

The Sponsor will supply paper diaries to all sites. Sites will dispense diaries to subjects at screening, Day 1, Day 14 and Day 29. Diaries will be collected on Day 1, Day 14, Day 29 and at follow-up.

At the Screening visit, subjects will be instructed how to complete the diary for an attack. While a subject has a diary in their possession, the subject will fill out the HAE attack diary daily, recalling whether symptoms of an HAE attack were experienced in the last 24 hours. Subjects must fill out the diary daily, regardless of the presence of HAE symptoms. If the subject does report an attack in their diary, additional details about the attack will be required, including location of the symptoms of the attack, severity, and treatment(s) administered and times of administration. During the treatment period, subjects will also record the time of day study drug was taken, and the number of capsules of study drug taken at each dose in the diary on a daily basis. Study drug doses administered in the clinic will be entered into the diary on site.

The Investigator (or designee) will proactively assess completion of the diary, during visits on Days 1, 7, 14, 21 and 29. While study staff are not permitted to make any entries into the diary, subjects may be asked to rectify incomplete diary entries made since the last visit/phone call based on outstanding questions a subject may have or incorrect assumptions/interpretation of diary questions.

Further training on completing the diary should be provided at each clinic visit or where required, during a telephone call.

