### **10.8.4. Attack Duration**

The duration of each confirmed attack will be calculated in hours, based on the start and stop date and time of the attack. For a confirmed attack that includes more than one subject-reported attack, the duration is calculated from the start of the first subject-reported attack to the end of the last subject-reported attack.

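### A missing attack stop date is set to 23:59 on the start date, which caps the attack below 24 hours and can contradict symptoms recorded in the daily diary

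*SAP*

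**What the plan says.** The rules for incomplete attack times are in SAP 10.1, under the heading on subject-reported attacks. If stop date and time are both missing: "The stop date will be set to the attack start date, the stop time will be set to 11:59PM". If only the stop time is missing, the reported date is kept: "The stop time will be set to 11:59PM". If the start time is missing: "The start time will be set to 12:00PM". If the start date is missing as well, it is taken from the diary day on which the attack question was answered Yes.

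SAP 10.8.4 defines the endpoint: "The duration of each confirmed attack will be calculated in hours, based on the start and stop date and time of the attack". Where adjudication combines several reports into one confirmed attack, "the duration is calculated from the start of the first subject-reported attack to the end of the last subject-reported attack".

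Duration of attacks is a secondary endpoint (Protocol 7.2.2, SAP 2.2.2). SAP 7.2 lists it for comparison of each dose with placebo if data permit, and SAP 12.1.4 summarises it by treatment group. SAP 12.1.4 also uses the attack end for intervals between attacks and as the censoring time for subjects who take no HAE medication.

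On the course of an attack, Protocol 5.1 describes rapid onset "with symptoms subsiding gradually over the following 3 to 5 days". Under Protocol 11.2.2 subjects complete the diary every day, "recalling whether symptoms of an HAE attack were experienced in the last 24 hours".

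**The concern.** An unknown end is replaced by the earliest calendar date on which the attack could have ended. The SAP already uses the daily diary answer to fill a missing start date, but not to fill a missing stop date, where the same source is available. The imputed end can therefore contradict the subject's own later entries. SAP 10.1 also handles adverse events and medications in the opposite way: a missing end day becomes the last day of the month.

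Three planned outputs are at stake. Duration is too short for an affected attack that ran past midnight. The interval to the next attack becomes too long. An untreated attack is censored too early in the time-to-medication analysis. The sensitivity analyses in SAP 12.1.3 concern the attack rate only, so no planned output would show how far imputed stops influence duration.

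**Working it through.** The plan states no figure for this rule, so there is nothing to reproduce. The check is clock arithmetic followed by a range under stated assumptions.

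**1. What the rule assigns (SAP 10.1).** Imputed duration = 23:59 − start time, on the start date.
- Start time also missing, 12:00PM read as noon: 23:59 − 12:00 = 11.98 h.
- Start time reported: 00:00 gives 23.98 h, 08:00 gives 15.98 h, 18:00 gives 5.98 h, 22:00 gives 1.98 h.
- Start times uniform over 24 hours (assumption): mean 12.0 h, 5th to 95th percentile 1.2 to 22.8 h. Uniform over 06:00 to 22:00: mean 10.0 h.

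Every value is below 24 h, so an unmerged attack that truly lasted 24 h or more is always shortened.

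**2. Error per imputed attack**, using the 12.0 h mean: 12 − D, where D is the true duration.
- D = 72 h: −60 h. D = 120 h: −108 h. These are the 3 to 5 days of Protocol 5.1.
- D = 24 h: −12 h. D = 12 h: about 0. D = 6 h: +6 h. These three values of D are assumptions.

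**3. Effect on mean duration.** With m the share of attacks lacking a stop date, change = m × (12 − D) hours, or m × (12 − D)/D as a proportion. The documents do not give m. The formula takes missingness as unrelated to attack length.

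| D | m = 2% | m = 5% | m = 10% | m = 20% |
|---|---|---|---|---|
| 12 h | 0 | 0 | 0 | 0 |
| 24 h | −0.2 h (−1.0%) | −0.6 h (−2.5%) | −1.2 h (−5.0%) | −2.4 h (−10.0%) |
| 72 h | −1.2 h (−1.7%) | −3.0 h (−4.2%) | −6.0 h (−8.3%) | −12.0 h (−16.7%) |
| 120 h | −2.2 h (−1.8%) | −5.4 h (−4.5%) | −10.8 h (−9.0%) | −21.6 h (−18.0%) |

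**4. The opposing rule.** When only the stop time is missing, moving it to 23:59 of the reported date lengthens the attack by about 12 h on average, for stop times uniform over the day. It cancels the error in step 3 when such attacks are (D − 12)/12 times as frequent as attacks with no stop date: 1 time at D = 24 h, 5 times at 72 h, 9 times at 120 h.

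**5. What is not touched.** The weekly rate in SAP 10.8.1 is attacks × 7 / days. It contains no stop time.

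**The case against.** The strongest reply is that the size is unknown and the natural comparator is doubtful. The 3 to 5 days is background disease description, while on study "each subject will continue to use their prescribed acute attack medication to treat any attacks". No passage gives a duration for treated attacks. If most end on the day they start, the rule does little harm or slightly lengthens them. This stands, and it is why the range must extend below 72 h.

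Three safeguards also stand. The imputation applies to each subject-reported attack. If a multi-day attack is entered on successive days and merged, a 23:59 stop on the last entry is close to the right answer. Staff check diary completion on Days 1, 7, 14, 21 and 29 and may ask subjects to rectify incomplete entries. Diaries collected on Days 14 and 29 are replaced at the same visits, so an ongoing attack can continue to be recorded. It is plausible that long attacks are the ones lacking a stop date, but the documents do not establish it.

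A reader might infer that imputed attacks all last about 12 hours. That is exact only when the start time is also missing. Otherwise 12 hours is an average under spread-out start times, with individual values from almost 0 to almost 24 hours.

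None of this justifies an imputed end that precedes days on which the subject recorded symptoms.

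**Conclusion.** The rule should be changed. For an unmerged attack that ran past midnight, the recorded duration is too short whatever the assumptions, and the diary may already hold a better end date. The consequence is confined to duration, between-attack intervals and the censoring time for first HAE medication.

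The size is conditional. It rests on an assumed 2% to 20% of stop dates missing, start times spread over the day, and an assumed true duration. The table above then gives a fall of about 1% to 10% at 24 h and about 2% to 18% at 72 to 120 h, no change at 12 h, and a rise for shorter attacks.

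Two stronger readings are not supported. One is that the duration endpoint as a whole is biased low: the missing share is not given, the stop-time-only rule pushes the other way, and merging can remove the error. The other is that the comparison with placebo is biased: that needs the share of missing stop dates, or the length of the attacks affected, to differ by arm, and nothing in the documents shows that it does.

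**What to change.** In SAP 10.1, replace the rule for a missing stop date and time with the following:
- Set the stop to 23:59 on the last consecutive diary day with symptoms recorded, counting from the attack start, and end it before the start of any separately reported next attack.
- Flag an attack still ongoing at the last diary as incomplete, instead of giving it a same-day end.
- Report the number of imputed stop dates by arm.
- Add a duration summary that leaves out imputed values.

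The cost is SAP wording and a small programming change on data already collected. SAP 11.3 already provides for refining missing-data rules. The downside is a possible overshoot of up to a day, because the diary question looks back 24 hours. The documents also do not show that a daily Yes is tied to a particular attack, which is why the cut-off at the next reported attack is needed.

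Censoring ongoing attacks in a Kaplan-Meier summary of duration is an option, but a debatable one: attacks cluster within subjects and the usual intervals would ignore that. The flag and the summary without imputed values are enough here.
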